## **13. Ethical consideration**

### **13.1 Informed Consent**

According to Regulation EU 2017/745, ISO 14155:2020 and applicable Bulgarian regulations, the Principal Investigator or his/her authorized designee must explain all aspects of the clinical investigation that are relevant to the subject's decision before any study procedure. In order to ensure

that the subject is fully informed the investigator must explain to each patient the nature of the clinical investigation, including any risks and benefits, its purpose and procedures, and expected duration of involvement in the clinical investigation. It must be made clear to the patient that participation in the clinical investigation is voluntary and a decision not to participate will not affect their right to the most appropriate treatment/care or affect the doctor-patient relationship. Participants will have the opportunity to carefully review the information document and ask questions prior to accepting or not to participate in the study. As this investigation is interventional, the consent shall be obtained in writing and the study participation must be documented in the patient medical file. Patients reserve the right to withdraw from the clinical investigation at any time, irrespective of their initial consent.

## 13.2 Subject confidentiality

The present study will be conducted under Regulation 2016/679/EU of the European Parliament and of the Council of 27 April 2016 on the protection of natural persons about the personal data and free movement of such data (GDPR) and PERSONAL DATA PROTECTION ACT, in force as from 1 January 2002.

In accordance with GDPR, the Sponsor is the “Controller” and the participating sites, monitors, data managers and statisticians are “Processors”. Lallemand Pharma AG, sponsor of the study, is responsible for the processing of the study data.

Confidentiality of data shall be observed by all parties throughout the clinical investigation. All data will be secured against unauthorized access. Subject names will not be sent to the sponsor. Only the patient number will be recorded in the e-CRF, and if the patient's name appears on any document, it must be obliterated before a copy of the document is supplied to the sponsor. All subject data that appear in reports and publications will be anonymised such that the privacy and confidentiality of each subject is maintained.

No data processing will be performed outside of the European Union.

To fulfil the requirements of source data verification, the PI will be required to obtain consent from each subject stating that they agree for their medical records to be accessed (this will form part of the consent process). To comply with GDPR, a specific document explaining the lawfulness of personal data processing conditions and patients' rights will be signed before any study procedure by the parents/guardians.

The patients' rights are the followings:

- The right to request access to, rectification, deletion or restriction of processing concerning personal data collected during the study,
- The right to get back all data linked to the research and to forward them to another data processing manager (portability right),
- The right to withdraw consent to data collection at any time and to request a restriction of processing concerning personal data as mentioned in GDPR's article 18. However, the data

processing manager keeps the ability to reject such request should this right likely make impossible or seriously compromise the achievement of the research objectives.

These rights can be exercised with the investigator or his designated representative or by contacting the Data Protection Officer appointed by Lallemand Pharma: [name], [[contact]](mailto:[contact]).

### **13.3 Insurance policy**

Lallemand Pharma AG has an insurance policy intended to guarantee against possible damage resulting from the investigation.

It is advisable to underline that non-compliance with the Research Legal Conditions is a cause for guaranteed exclusion.

## **14. Vigilance**

### **14.1 General**

Healsea® Rescue\* will be used in the intended use covered by the CE mark in this PMCF study.

Pursuant to (EU)2017/745 Medical Device Regulation, for a post market clinical follow-up investigation of a medical device used within the intended use covered by the CE-mark, requirement of MDR articles 87 to 90 apply (materiovigilance).

Nevertheless, if a causal relationship between a serious adverse event and an investigational procedure has been established, the safety reporting laid down in Article 80 of the MDR. Since the electronic system referred to in Article 73 (Eudamed) will not be available and fully functional at the date of study start, the procedures for safety reporting will be performed according to modalities described in the MDCG 2020-10/1 and -10/2.

All modalities of safety reporting will be detailed in a Safety Management Plan signed by the sponsor vigilant, the Principal Investigators, the local CRA in charge of the monitoring and a representant of the CRO.

### **14.2 Definitions**

**Incident** means any malfunction or deterioration in the characteristics or performance of a device made available on the market, including use-error due to ergonomic features, as well as any inadequacy in the information supplied by the manufacturer and any undesirable side-effect (MDR 2017/745).

**Serious incident** means any incident that directly or indirectly led, might have led or might lead to any of the following: (a) the death of a patient, user or other person, (b) the temporary or permanent

serious deterioration of a patient's, user's or other person's state of health, (c) a serious public health threat (MDR 2017/745).

**Serious public health threat** means an event which could result in imminent risk of death, serious deterioration in a person's state of health, or serious illness, that may require prompt remedial action, and that may cause significant morbidity or mortality in humans, or that is unusual or unexpected for the given place and time (MDR 2017/745).

#### **Expected and foreseeable side effects (MEDDEV 2 12-1 rev. 8)**

They meet all the following criteria:

- Clearly identified in the manufacturer's labelling,
- Clinically well known as being foreseeable and having a certain qualitative and quantitative predictability when the device is used and performs as intended,
- Documented in the device master record, with an appropriate risk assessment, prior to the occurrence of the incident and,
- Clinically acceptable in terms of the individual patient benefit.

**Adverse event** means any untoward medical occurrence, unintended disease or injury or any untoward clinical signs, including an abnormal laboratory finding, in subjects, users or other persons, in the context of a clinical investigation, whether related or not related to the investigational device (MDR 2017/745).

Adverse or intercurrent events are graded as follows:

- Mild: Awareness of signs or symptoms but easily tolerated.
- Moderate: Uncomfortable enough to cause interference with usual activity.
- Severe: Incapacity with inability to work or do usual activity.

#### **Serious adverse event (SAE) (MDR Article 2(58):**

Any adverse event that led to any of the following:

- a) death,
- b) serious deterioration in the health of the subject, that resulted in any of the following:
  - i. life-threatening illness or injury,
  - ii. permanent impairment of a body structure or a body function,
  - iii. hospitalisation or prolongation of patient hospitalisation,
  - iv. medical or surgical intervention to prevent life-threatening illness or injury or permanent impairment to a body structure or a body function,
  - v. chronic disease,
- c) foetal distress, foetal death or a congenital physical or mental impairment or birth defect

### **14.3 Reporting in the eCRF**

At V2, the investigator will validate the adverse events/incidents and concomitant medications reported in the e-diary by questioning the patient.

All serious and non-serious incidents/serious and non-serious risk of incidents/expected side effects /serious and non-serious adverse event (pertinent in the context of the common cold, additional study procedures and of the medical device use) occurring during the clinical investigation will be reported in the e-CRF.

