**D1-D8 (at home):**

The patient will be asked to complete the electronic diary daily (WURSS-21 assessed once daily in the evening, taking into account the symptoms from the morning to the evening, adverse events/incidents/expected undesirable side effects and concomitant medications).

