**D9-D13/15 (at home):**

Patients will continue to complete the electronic diary daily (incidents/adverse events in relation with the common cold, concomitant medications). The patient for whom common cold symptoms persist, will be instructed to continue to complete the WURSS-21, until the subject feels not sick for two consecutive days.

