**Visit 2 (V2) – (Day 13-15): end of study**

The investigator or his/her delegated designee will:

- Perform a physical and clinical examination. A pharyngeal nasal swab will be performed by the investigator or by the delegated study nurse to check for absence or presence of SARS-CoV2.
- Validate adverse events pertinent in the context of the common cold and of additional study procedures /incidents linked to medical device use and concomitant medications reported in the e-diary and complete the e-CRF accordingly and report any new relevant safety events.
- Ask the patient to complete the WURSS-21 if he/she still has symptoms.
- Assessed the compliance to the treatment by weighting the device returned by the subject. In case of nasal spray dysfunction and attribution of a new treatment using the back-up randomization list, the compliance will be assessed by weighting both devices. If a nasal spray is lost, the investigator will ask the patient to specify the number of missed nasal spray use and will report the data into the e-CRF.
- Ask the patient to complete a satisfaction questionnaire.

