### 9.1 Source documents

The source documents (e.g., medical file, clinical and office charts, log for compliance data...) which contain the source of data recorded in the CRF should be specified. The e-diary will be used as source document for WURSS-21, concomitant treatments and adverse events/incidents reported by patient.

Each subject will be assigned and identified by a unique screening number. Any reference made to an individual subject within the study must be done using the unique screening number.

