#### 10.4. Non-related adverse events

In the following paragraph, for a smoother reading:

- adverse events will be referred as AE;
- treatment-emergent adverse events will be referred as TEAE.

Adverse events are coded using the MedDRA dictionary version 25.0. They are classified by System Organ Class and Preferred Term.

For efficacy analyses, only non-related AEs are considered, i.e. adverse events with a relationship to study device equal to “not related”. These analyses will be performed on the Safety Set.

An adverse event will be considered as a treatment-emergent adverse event (TEAE) if:

- it was reported at least one day after screening;
- it was not present prior to the reference start date;
- it was present prior to the reference start date and worsened during the study (increase of intensity);
- it reappears after the reference start date (finished before the reference start date).

Missing or incomplete dates will be estimated as described in §6.4.4 in order to determine the TEAEs, but they will be presented as reported in CRF in the data listings. Generally, an adverse event for which the onset date is missing or incomplete and does not permit to identify the onset according to the date of the reference start date (i.e. missing onset day and month/year corresponding to the reference start date) will be considered as treatment-emergent.

Note: if the intensity/severity is missing, a conservative approach will be adopted and the intensity/severity will be considered as severe.

A given treatment-emergent adverse event (according to the MedDRA terminology) will be counted only once per subject. If a subject experienced several AEs in the same SOC/PT, the most severe intensity will be retained for this SOC/PT.

- Summary of non-related adverse events

A summary table will be produced:

- number and percentage of subjects with at least one non-related adverse event (AE);
- number and percentage of subjects with at least one non-related AE leading to definitive study device discontinuation;
- number and percentage of subjects with at least one non-related AE leading to definitive study discontinuation;
- number and percentage of subjects with at least one non-related TEAE.

The number of non-related AEs of each category will also be provided in this table.

- Analysis of non-related treatment-emergent adverse event

---

The number and percentage of subjects with non-related TEAEs will be summarised by System Organ Class and Preferred term.

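### Entry of adverse events in the eCRF, serious ones included, depends on an undefined judgement of pertinence, which contradicts the protocol's own adverse event definition and its promise to list every event

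*Protocol*

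**What the plan says.** **Definition and promise.** Under Protocol 14.2 an adverse event "means any untoward medical occurrence, unintended disease or injury or any untoward clinical signs", and the definition goes on to apply "in the context of a clinical investigation, whether related or not related to the investigational device". Protocol 8.4 (Safety) undertakes to list all adverse events, incidents and expected side effects, and to summarise the treatment-emergent ones.

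**Entry in the eCRF.** Protocol 14.3 attaches a condition to adverse events, serious and non-serious: they are to be "pertinent in the context of the common cold, additional study procedures and of the medical device use". Protocol 7.4.1 (Visit 2) repeats it. The investigator is to "Validate adverse events pertinent in the context of the common cold and of additional study procedures", together with device-linked incidents, complete the eCRF accordingly, and add any new safety events considered relevant. Neither section says how pertinence is decided, and neither exempts serious events.

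**What patients are asked to report.** For D1-D8, Protocol 7.4.1 has the diary collect "adverse events/incidents/expected undesirable side effects and concomitant medications", without restriction. For D9-D13/15 the same section asks for "incidents/adverse events in relation with the common cold, concomitant medications". The synopsis, the flow chart (Protocol section 2) and SAP section 3 describe adverse event reporting in that later period with no link to the cold.

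**Transfer from diary to eCRF.** Protocol 9.1 states: "The e-diary will be used as source document for WURSS-21, concomitant treatments and adverse events/incidents reported by patient". Protocol 9.2 has diary adverse events uploaded to the eCRF automatically. Protocol 7.1.4 has the investigator validate them at Visit 2 before they are reported in the eCRF.

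**Analysis.** SAP 10.4 states: "For efficacy analyses, only non-related AEs are considered". It tabulates these events by arm on the Safety Set. SAP 11.2 limits the safety section to events with some relationship to the device.

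**The concern.** A condition on what enters the database works differently from a condition on what is analysed. Once an event is left out of the eCRF, no table or listing can bring it back, and a reader of the report cannot tell that it is missing. Here the condition is a judgement made one patient at a time, against a criterion the protocol does not define.

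The safety objective (Protocol 6.3) covers systemic as well as local tolerance, while the only expected event is local itching and irritation (Protocol 5.2). An unexpected systemic effect may not be recognisable in a single patient. Comparing arms is the way to find it, and that needs events recorded before anyone decides what they are linked to. At stake are the completeness of the SAP 10.4 tables and the full listing promised in Protocol 8.4. The tracking of unreported adverse events in Protocol 5.5.3 is also affected: with pertinence undefined, an event that was missed cannot be told apart from one that was set aside.

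**Working it through.** The plan gives no figure to reproduce on this point. The check sets the passages side by side.

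1. **Definition against entry rule.** Protocol 14.2 covers any untoward occurrence, related or not. Protocol 14.3 and the Visit 2 instructions cover pertinent ones. The entry rule is narrower than the definition, so the listing in Protocol 8.4 cannot be guaranteed complete.

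2. **Days 9 to 13/15.** Protocol 7.4.1 ties diary reporting to the cold. The synopsis, flow chart and SAP section 3 do not. Protocol 14.3 covers the whole investigation and includes procedure and device events. The diary instruction is thus narrower than every other description of that period.

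3. **Can a diary event be dropped?** Under Protocol 9.2 it uploads automatically. Under Protocol 7.1.4 it is validated first. With the Visit 2 condition, the second route can lose an event and the first cannot. The documents do not say which one governs.

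4. **Tracing one event.** Take a serious event in the follow-up period that is judged unrelated to the device, the procedures and the cold.
   - Diary: the D9-D13/15 instruction in Protocol 7.4.1 does not ask for it.
   - eCRF: Protocol 14.3 does not require it.
   - Primary Notification Form (Protocol 14.4.1, Appendix B): meant for incidents and expected side effects.
   - SAE form (Appendix C): used when a causal link with a study procedure is suspected. Protocol 14.4.2 excludes the not-related level from reporting, although it also says that each serious adverse event is classified for causality, which presupposes that each one is captured.
   - Analysis: if it is entered anyway, the SAP 10.4 summary and its mock table (Table 14.2.4.1.1) have rows for any event, device discontinuation, study discontinuation and treatment-emergent events. There is no row for serious events. SAP 11.2 does not count it, because it is not device-related.

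5. **Size, as an illustration only.** The documents give no adverse event rate and no share of events judged not pertinent. Assume an event with incidence p = 0.03 (not from the documents), 100 treated patients in an arm (Protocol 8.5, if all randomised patients use the spray), and a share s of such events that passes the entry condition. The probability of at least one recorded event is 1 − (1 − p·s)^100:
   - s = 1: 1 − 0.97^100 = 0.95
   - s = 0.5: 1 − 0.985^100 = 0.78
   - s = 0.1: 1 − 0.997^100 = 0.26

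   This shows how the result depends on s. It does not estimate s.

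**The case against.** A reader might infer that events outside the three categories are never recorded. The documents do not support that. Throughout the treatment period (D1-D8) the diary takes adverse events without restriction, the diary is source data, and Protocol 9.2 says its events upload automatically. SAP Listing 16.2.7.1 is also unrestricted. For those days the open question is whether an event survives validation at Visit 2.

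A reader might also infer that the rule screens out suspected device effects. It does not. Protocol 14.2 counts any undesirable side effect as an incident. On the natural reading of Protocol 14.3 the pertinence condition qualifies adverse events, not incidents, and Protocol 14.4.1 has incidents notified within 24 or 48 hours. The condition is wider than device-relatedness too: an event unrelated to the device but pertinent to the cold is entered and tabulated under SAP 10.4. What remains exposed is an event that the investigator links to none of the three.

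Three further points stand. The Safety Management Plan (Protocol 14.1), which is not among the documents, may say how pertinence is applied. The judgement is made under blinding and in both arms, so a bias in one direction is not shown. And full recording would not make a rare event stand out in a test: 3 of 100 against 0 of 100 gives a one-sided Fisher p of (100·99·98)/(200·199·198) = 970,200/7,880,400 = 0.12. The loss is one of completeness.

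None of this removes the stated entry rule, its conflict with Protocol 14.2 and 8.4, or the missing route for the serious event traced above.

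**Conclusion.** The point holds as an inconsistency with a practical consequence. The protocol defines adverse events broadly, promises to list them all, and then makes eCRF entry depend on an undefined judgement that applies to serious events as well. In D9-D13/15, Protocol 7.4.1 also narrows what patients are asked for. Events judged not pertinent may therefore be absent from the validated data and from the SAP 10.4 tables, in an unknown number. The documents do not support saying that many events are removed, or that the chance of recording an unexpected one is close to zero; both would require a filtered share that they do not give.

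The conclusion assumes that investigators follow Protocol 14.3 and the Visit 2 instructions as written, and that no unseen document overrides them. If Protocol 9.2 governs and uploaded events stay in the database, the D1-D8 part of the problem largely disappears. The narrower diary instruction after Day 8 and the missing serious-event row would remain. The primary efficacy analysis is not affected. The matter should still be corrected, because safety data lost at entry cannot be recovered in the analysis.

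**What to change.** - Remove the pertinence condition from Protocol 14.3 and from the Visit 2 instructions in 7.4.1, and remove the link to the cold from the D9-D13/15 diary instruction, so that it matches the synopsis, the flow chart and SAP section 3.
- Enter every adverse event from D1 to V2 in the eCRF, with seriousness, intensity and relationship. If the sponsor wants to keep pertinence, record it as an attribute, not as a condition of entry.
- Reconcile Protocol 7.1.4 with 9.2. State whether diary events upload before or after validation, and that validation may annotate or correct an event but not remove it without trace.
- Add a serious-event row to the SAP 10.4 summary and to mock Table 14.2.4.1.1.
- Bring the Safety Management Plan into line. The scope of expedited reporting stays as it is.

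The cost is a wording amendment, one table row and a few more eCRF entries. The e-diary already exists and each patient is followed for at most 15 days.

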### **14.4 Investigator's responsibilities and processing timelines**

#### **14.4.1 Materiovigilance**

All incidents and expected undesirable side effects will be reported to LP vigilance manager according to MDR, MEDDEV 2.12 rev 8 modalities, national requirements, ISO 14155:2020 and Lallemand Pharma procedures which are described in the safety management plan. This document will be signed by the Principal Investigator, representants of the Clinical Research Organization (CRO), CRA in charge of the monitoring and the Vigilant Manager, before the study start.

As soon as the investigator will be informed of the event, he/she will complete a Primary Notification Form template (PNF, appendix B) and send it to the sponsor ([[contact]](mailto:[contact]) and/or [contact] (as back-up method) and to the Vigilance manager [name] ([[contact]](mailto:[contact])), to the CRO ([[contact]](mailto:[contact]) and/or [contact]), to the EU representative [name] ([[contact]](mailto:[contact])), and to the local CRA ([[contact]](mailto:[contact])) with any relevant supportive documentation within the same day (<24h) for serious (risk) incident and within two calendar days (<48h) for non-serious incidents and expected side effects.

